**General Safety:**

1. ADE (adverse device effect) and AE (adverse event) tracking twice daily via a safety in-use diary. We will list a summary of the product related ADE and AEs for both treatment periods and the PI, Sub-PI, Statistician and Clinical Scientist will make a recommendation whether the product safety of Ninjamas is comparable to current product based on the medical and clinical evidence of the reported AE and ADE data.

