## 2. Objectives

The primary objective of this clinical trial is to confirm the in-use tolerability of the Ninjama EU overnight pant product, in the target population of bedwetters aged 4-7 years, based on a body of evidence from clinical assessments of skin, adverse events and parent/child perception data. This data will be part of the clinical evidence in the Clinical Evaluation Report needed to market this product as a Class 1 Medical Device in the EU, confirming that the product is safe to use and performs within its intended purpose.

The secondary objective is to understand the clinical benefit of the NJ EU overnight pant product in a bedwetting population aged 4-7 years, based on [REDACTED] waking up in a dry bed, via collecting H&P and parent/child perception data in diaries and end-of-use questionnaires.

[REDACTED]

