- Child Perception: Child will be asked simple yes/ no questions to determine if they feel irritation [REDACTED]. If yes, the parent/legal guardian will ask the child to point to location where they feel the irritation [REDACTED].

- [REDACTED]

- [REDACTED]

Up to 30 children (approximate split of 15 males and 15 females) who meet inclusion/exclusion criteria will be enrolled in the clinical trial. S7 children will be enrolled in this clinical trial because nocturnal enuresis is most prevalent in children aged 4-7 and the pant design for S7 and S8 products are similar. Therefore, the data generated for the S7 population can be used to support the S8 population. Children for this clinical trial will be enrolled by North Cliff Consultants in Cincinnati, USA. Eligible subjects will be bedwetters who have wet the bed at least once a week or more over the past 3 months. The children should be accustomed to wearing an absorbent pant product overnight. They will be asked to use their own overnight pant every night for 3 weeks of the clinical trial and will be asked to use the NJ EU test pant every night for the other 3 weeks of the clinical trial. The order of the NJ EU product and own product will be randomized. Parents will

be asked to refrain from using wet wipes to clean the child's skin for the duration of the clinical trial (no test wipes will be provided).

If a subject drops out of the clinical trial, they will not be replaced, due to the short duration of the clinical trial.

Once qualified, parent/legal guardian will be asked to pick up the equipment [REDACTED] [REDACTED] from North Cliff Consultants. They will receive training on how to handle the equipment and how to complete the questionnaires. Parent/legal guardian will be required to begin with the clinical trial after the training session. They will be given 2 days to practice [REDACTED] before data is officially collected for the clinical trial.

Parent/legal guardian will be instructed to complete a digital questionnaire twice daily (once in the morning before removing the used pant and once in the evening when applying the fresh pant) [REDACTED]. This will include taking four photos of the child wearing the pant (front, back and both hips) [REDACTED].

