### **3.5.2 Replacement of Subjects**

If a subject drops out of the clinical trial, they will not be replaced, due to the short duration of the clinical trial.

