### **4.2 Determination of Sample Size**

This data will be used to bridge to a wealth of existing P&G Baby and FemCare AI clinical trial data, therefore sample size was based on practical limitation, not on statistical considerations.

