**Attachment B**  
**Statistical Analysis Plan**

**Study Populations**

The Intent-to-treat (ITT) population is defined as all subjects who experienced the application of the assigned study product. The Per Protocol (PP) population includes subjects in the ITT population who have no serious inclusion/exclusion violations, no serious continuance criteria violations, no serious concomitant medication violations, and high study product compliance. The ITT population will be used for the safety analysis. Analyses of the Per Protocol population will be done to better understand the data.

Prior to the statistical analysis, all data will be checked for accuracy, completeness, and compliance to the study protocol. Subject evaluations will be checked for compliance to the study protocol regimen and subjects will be assessed for compliance to the protocol inclusion/exclusion criteria. Additionally, investigator comments will be assessed for extraneous factors that could affect the usefulness of the subject's data. Non-evaluatable observations and the rationale, along with the method for handling the observations will be documented by the sponsor prior to analysis of the data.

Period and carryover effects will be evaluated for potential influence on the results. Means will be plotted by periods to understand these effects.

Summary descriptive statistics will be provided for all parameters. Ninety-five percent confidence intervals (CIs) will be constructed for all clinical assessments for each treatment code. Any data reported as 'unable to evaluate' will be treated as missing and excluded from the analysis.

The methods used for the analysis will include but not be limited to a variety of parametric and non-parametric statistical methods based on the distribution/characterization of the data.

The following endpoints will be investigated.

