**Revised Wording:**

This will be a single center, single blinded (sponsor's statistician and substitute clinical scientist for the evaluability meeting will be blinded to the product codes), randomized, cross-over, IRB-Approved, in-home clinical test design over 6 weeks, with two usage periods of 3 weeks each.

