**Revised Wording:**

Approximately 32 children (approximate split of 16 males and 16 females) who meet inclusion/exclusion criteria will be enrolled in the clinical trial.

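### SAP item 1 asks for a recommendation on comparable safety from a summary of events in about 32 children, without tying it to what those data can exclude

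*Combined protocol and SAP*

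**What the plan says.** In Attachment B, General Safety item 1, adverse events and adverse device effects are tracked twice daily, and a summary of the product-related ones is listed for both treatment periods. The principal investigator and sub-investigator, with the "Statistician and Clinical Scientist will make a recommendation whether the product safety of Ninjamas is comparable to current product", judge on the medical and clinical evidence of the reported events. Item 1 shows no redaction. It states no margin, no rate and no interval. By contrast, item 2 (leaks) does carry a not-worse-than criterion, whose size is blacked out.

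Other parts of the plan bear on this:

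- Attachment B, Study Populations, promises descriptive statistics for every parameter, and "Ninety-five percent confidence intervals (CIs) will be constructed for all clinical assessments for each treatment code".
- Section 4.2 says that "sample size was based on practical limitation, not on statistical considerations", because the data are meant to bridge to existing trials.
- Section 2 makes adverse events one of three strands of the primary objective. The data are to form part of the Clinical Evaluation Report, "confirming that the product is safe to use and performs within its intended purpose".
- Amendment 1 sets the size: "Approximately 32 children (approximate split of 16 males and 16 females) who meet inclusion/exclusion criteria will be enrolled".

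**The concern.** A recommendation that safety is comparable is a positive claim of similarity. To support it, the data must rule out a difference large enough to matter. Item 1 goes from a summary of events to that recommendation without asking what the summary can rule out. With about 32 children, a short or empty list fits a safe product, but it also fits a product whose device-effect rate is appreciable.

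A short list is also likely for a reason unrelated to the comparison. Under Section 7.5.1, ordinary irritation in the pant area is not recorded as an adverse event or device effect unless it leads the parent to seek medical attention.

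An unquantified statement of comparability could then pass into the Clinical Evaluation Report. It could also pass into the compliance statement in Attachment A, which is to be updated from this trial's outcome.

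**Working it through.** The plan states no event rate, margin, power or precision for safety, so there is no figure of its own to reproduce. The check asks what a sparse list can exclude.

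**Inputs**

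- Children: 32 (Amendment 1). The body of Section 3.1 still prints "Up to 30 children (approximate split of 15 males and 15 females"), so 30 is shown as well.
- Exposure: an "in-home clinical test design over 6 weeks, with two usage periods of 3 weeks each". Each child is planned to use both products, so a rate below means the proportion of children with at least one device effect in a three-week period.
- Dropout: "If a subject drops out of the clinical trial, they will not be replaced". No rate is given; 28 exposed children is an assumption for illustration.

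**1. Upper limit for one product.** With no child affected, the exact limit solves (1 − p)^n = α, so p = 1 − α^(1/n), with α = 0.05 (one-sided) or 0.025 (two-sided 95%).

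- n = 32: 1 − 0.05^(1/32) = 8.9%; 1 − 0.025^(1/32) = 10.9%
- n = 30: 9.5%; 11.6%
- n = 28: 10.1%; 12.3%

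With x affected children, the limit is the 0.95 or 0.975 quantile of Beta(x + 1, n − x). At n = 32:

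- x = 1: 14.0% one-sided; 16.2% two-sided
- x = 2: 18.4% one-sided; 20.8% two-sided

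**2. Upper limit for the within-child difference, no event on either product.** With no discordant child, the squared paired score statistic at a true difference d is n·d/(1 − d). Setting it equal to 1.96² = 3.8416 gives d = 3.8416/(n + 3.8416).

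- n = 32: 3.8416/35.8416 = 10.7 points
- n = 28: 3.8416/31.8416 = 12.1 points

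**3. Chance of an empty test-pant list among 32 children, for assumed true rates**

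- 2%: 0.98^32 = 52%
- 5%: 0.95^32 = 19%
- 10%: 0.90^32 = 3%

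**4. Scale.** To exclude 5% with no events takes ln 0.05/ln 0.95 = 58.4, so 59 children (one-sided), or ln 0.025/ln 0.95 = 71.9, so 72 children (two-sided). This is context only, not a case for a larger trial.

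**5. Do the SAP's general intervals already cover this?** The sentence on intervals comes before the endpoint list, and that list begins with events, so events could be meant. Section 2, however, names skin assessments and adverse events as separate strands, so events could equally be left out. Under either reading the intervals are per product. No interval for the difference is stated, and none is linked to the recommendation.

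**The case against.** The strongest reply is that item 1 asks for a clinical judgement, not a statistical decision. The panel is asked whether safety is comparable, so it may answer that the data are too sparse. A reader might infer that the plan obliges the panel to call a short list comparable. The text does not say so; it permits that conclusion and contains nothing to prevent it.

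A reader might also infer that event data get nothing beyond a list. That goes too far: descriptive statistics are promised for all parameters, and the sentence on intervals is ambiguous rather than silent.

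It is tempting to quote the miss rate of a paired significance test, or the pass rate of a rule such as at most one more affected child on the test pant. The SAP contains neither rule, and the results depend on the rates assumed. At 32 children, with events independent within child, that second rule passes 5% against 1% in 60% of trials, but 10% against 2% in only 29%. Such figures do not describe this plan.

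Finally, this is openly bridging evidence, and events are one of three strands. Skin rash and irritation are analysed under their own items, whose criteria are largely blacked out. Item 1 alone does not carry the claim that the product is safe.

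All of this limits the point without removing it. A bridging role argues for stating plainly what these data can and cannot exclude.

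**Conclusion.** The point holds as a gap between the data and the wording of the conclusion. Item 1 allows a sparse list to be reported as comparable safety without saying what the list excludes. At 32 children, zero device effects on the test pant leave true rates up to 8.9% (one-sided) or 10.9% (two-sided) unexcluded, and zero on both products leaves an excess of up to 10.7 points. One affected child raises the two-sided per-product limit to 16.2%. The 9% to 11% range therefore applies to zero events only.

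The limits assume that all 32 children are exposed to the product concerned, and complete both periods for the paired figure; fewer children widen them. The chances of an empty list rest on assumed rates, since the plan gives none.

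This is not a finding that the trial failed a power calculation, because none was claimed. Nor does it show that the test pant is less safe. The contents page lists Amendment 2, but its text is not in the material reviewed, so a later change to item 1 could not be checked.

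**What to change.** Amend item 1 of the SAP as follows.

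1. For each product, report the number and percentage of children with at least one product-related event, with an exact (Clopper-Pearson) 95% interval, including when the count is zero. Show adverse events regardless of causality separately, so that colds and injuries do not blur the device comparison.
2. Report the within-child difference, test minus own product, in the proportion of children with a product-related event, with a paired 95% score interval.
3. Require the panel's recommendation to state the upper limits from 1 and 2. Add that few or no events do not by themselves establish comparable safety.

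The panel still reviews each event medically and still makes its recommendation. The change needs a few sentences and one small table from data already collected, with no extra children or procedures. The price is a less favourable headline: at best an upper limit of about 9% to 11% at 32 children, and a higher one if any event occurs.

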1. This group will be easier to recruit with approximately 10-25% of the population suffering from nocturnal enuresis at age 4-7, compared to only 1-5% of the population at age 8-12. In addition, the willingness of younger children to participate in a bedwetting clinical trial where the parent needs to do measurements in the pant area will be higher than for older children, who may not want the parent in the room when they remove their pant.
2. Traditionally children are not considered for treatment of bedwetting until age 7. Over the age of 7 the child is usually treated with drug therapy to reduce urine production at night.
3. The S7 and S8 NJ EU pants have the same design, with S8 having a more absorbent capacity and a bigger fit.

[REDACTED]

[REDACTED]

5. Younger children are more likely to wait for a parent to assist with dressing and will therefore wear the wet pant longer than an older child, who is more likely to remove the pant themselves. Younger children also have a higher risk of feces on the skin (which is an irritant for the skin) as they are not well-practiced in wiping themselves clean after visiting the toilet. Therefore, the S7 group has more risk of developing rash from wet pants than the S8 group, because their skin is wet longer and any feces resting on the skin can result in compromised skin and rash in the pant area.

Our focus will be on children with monosymptomatic enuresis i.e., enuresis in children without any other lower urinary tract symptoms (e.g., increased frequency, daytime incontinence, urgency, genital, or lower urinary tract pain) and without a history of bladder dysfunction.

This clinical trial will accept children with both primary and secondary enuresis. Primary enuresis means the child has never had a dry period at night. Secondary enuresis means the child developed nocturnal enuresis after being dry for a period of at least six months.

This clinical trial will be a 6-week, in-home clinical trial to understand the safety, performance, and impact on skin of the NJ EU pant compared to the child's currently used absorbent pant or diaper product.

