## 3. Investigational Plan

### 3.1 Clinical Trial Design

This will be a single center, single blinded (sponsor's team will be blinded to the product codes), randomized, cross-over, IRB-Approved, in-home clinical test design over 6 weeks, with two usage periods of 3 weeks each. During one period the child will maintain usage of their usual absorbent night pant/diaper and during the other usage period they will use the NJ EU absorbent pant. We will track habits and practices that may impact skin health and product performance as well as medication use and Adverse Events/ Adverse Device Effects (AEs /ADEs). Children will be asked to wear either their own pants or the test pants exclusively at night and parent/legal guardian will be asked to collect data in the evening before bed and in the mornings after getting up.

Parent/Legal Guardian will be trained to execute the measurements on their own child for the following reasons:

1. Children this age are usually told not to let strangers touch them in the genital and buttock area, so we want to avoid telling kids it is OK in this case. We will ensure that the child is comfortable to participate in this clinical trial and can at any time end their participation in this clinical trial should they feel uncomfortable.
2. Due to COVID restrictions, clinical trial personnel should minimize close contact with panelists as much as possible, especially with children under 5 years of age, who cannot be vaccinated. We will therefore ask the trained parent/legal guardian to do the measurements on his/her own child/ren. Children can stop the study procedures at any time if/when they feel uncomfortable.

This clinical trial is designed to track the following:

- general safety (AEs and ADEs),  
[REDACTED]
- assess fit and performance of the overnight pant products (fit images, leaks, [REDACTED])

The following table shows which endpoints will be measured at which time and where on the child:

Endpoint	When Measured	Where Measured
Leaking & Pant Fit	Before pant removal	Waist front and back, crotch area, leg cuffs
Child skin irritation perception	Directly before removing pant	Entire pant area
AE, ADE, [REDACTED]	Observed all the time and reported twice a day	Observe child and pant

[REDACTED] Leaking and Pant Fit: Mobile phone images of the pant on the child will be collected by the parent/legal guardian at home [REDACTED]

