#### **7.5.1 Adverse Event and Adverse Device Effect Reporting**

[REDACTED] the parent/legal guardian will be asked twice daily about their child's health and medication intake. Based on the information provided, Sponsor and PI will determine if it is appropriate to record as an Adverse Event or Adverse Device Effect and will contact the parent/legal guardian for more information. Such an occurrence does not necessarily have to have a causal relationship with product use. Due to the nature of this clinical trial, skin irritation in the pant area (diaper rash) will not be documented as an Adverse Event or Adverse Device Effect given it is one of the end points of interest for the clinical trial. However, if a skin reaction occurs in the pant area which causes the parent/legal guardian to seek medical attention, outside the normal follow-up given to the child within the clinical trial, this will be documented and followed in the same manner as other Adverse Events or Adverse Device Effects.

[figure not shown]
The Investigator or designee will review each Adverse Event Report and complete the form based on the following decision charts:

*Chart 1: Categories of ADE and AEs*

Adverse events	Non-device-related	Device- or investigational procedure-related	
Non-serious	Adverse event (AE) a (3.2)	Adverse device effect (ADE) c (3.1)	
Serious	Serious adverse event (SAE) b (3.45)	Serious adverse device effect (SADE) (3.44)	
		Anticipated	Unanticipated
		Anticipated serious adverse device effect (ASADE) c (3.1, Note 1 to entry)	Unanticipated serious adverse device effect (USADE) (3.51)

a Includes all categories.  
b Includes all categories that are serious.  
c Includes all categories that are related to the device or the investigational procedure.

Chart 2: AE categorization flow chart

The Investigator or designee will review each Adverse Event Report and complete the form based on the following definitions:

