**Attachment A****Risk Assessment****Product Safety**

No safety issues are anticipated with this clinical trial as outlined. Children participating in this clinical trial are using marketed products or products that are close to being marketed. From products purchased on the market, we can assume that they have been tested and evaluated for their safety in daily use. Children will be asked to use these products as intended.

For the NJ EU test products, a full risk assessment according to the ISO 14971 standard is being conducted and will be summarized in a separate document before the start of the clinical trial.

The P&G company has a 20+ year history of baby diaper clinical data (0-36 months) to show that our diaper and pant technology is safe to use and effective for managing urine gushes in a baby and toddler population. The P&G company also has adult (18+ years) female incontinence products in the EU market, including absorbent heavy incontinence pants, that are classified as Class 1 Medical Devices, which were demonstrated to be safe to use and effectively manages urine gushes of adults as seen in the statement of compliance from the CER report dated Feb 2020 [1].

[REDACTED] P&G markets a training pant (BabyDry Pants S7) in the EU. Based on the Post Market Safety Surveillance data of similar products in the EU and US market (BabyDry Pants, FemCare AI Pants, [REDACTED]), we have reason to believe that the NJ EU product will have no safety related issues when used as an overnight pant for children aged 4-12 years, based on skin and health related AEs. [2]

Based on our current knowledge about this product and similar marketed products, we conclude the following statement, which will be updated based on the outcome of this clinical trial:

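### SAP item 1 draws a conclusion on comparable product safety from AE/ADE data that, by rule, leave out most pant-area rash, and no visible text adds the skin results or narrows the conclusion

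*Combined protocol and SAP*

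**What the plan says.** **The recommendation.** Attachment B, General Safety, item 1 summarises product-related ADEs and AEs for both treatment periods. The principal investigator, sub-investigator, statistician and clinical scientist then recommend whether the product safety of the test pant is "comparable to current product based on the medical and clinical evidence of the reported AE and ADE data". Item 1 names no other evidence.

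**What those data contain.** Section 7.5.1 states that "skin irritation in the pant area (diaper rash) will not be documented as an Adverse Event or Adverse Device Effect", and gives as its reason that rash is an endpoint of the trial. The one exception is a skin reaction in the pant area "which causes the parent/legal guardian to seek medical attention, outside the normal follow-up given to the child within the clinical trial".

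**Where rash is analysed.** Attachment B, Skin Health, covers parent-graded rash (item 6) and irritation reported by the child (item 10). Their comparison rules are largely redacted.

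**The primary objective.** Section 2 seeks to confirm in-use tolerability "based on a body of evidence from clinical assessments of skin, adverse events and parent/child perception data".

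**The concern.** The label on item 1's conclusion is product safety, but the evidence that item 1 names excludes most of the one kind of harm the protocol expects. Attachment A anticipates no risk to subjects beyond skin reactions such as redness. The Introduction, in explaining the choice of age group, says that "the S7 group has more risk of developing rash from wet pants than the S8 group".

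The trial feeds the Clinical Evaluation Report (section 2), and Attachment A contains a safety statement "which will be updated based on the outcome of this clinical trial". If item 1 is followed as written, the team could record that product safety is comparable while rash that never led to outside care was worse on the test pant. A reader of that sentence would not see that such rash had been left out.

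**Working it through.** The plan gives no rash rate, care-seeking share, margin or count rule for item 1, so there is no figure to reproduce and no arithmetic that would not rest on invented inputs. The check sets the passages side by side.

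**Step 1. Compare the evidence base of the objective with that of item 1.**

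| Evidence strand in section 2 | Used in item 1? | Where it is analysed |
|---|---|---|
| Skin assessments | Not named | Skin Health, item 6 (rash) |
| Adverse events | Yes | General Safety, item 1 |
| Parent/child perception | Not named | Skin Health, item 10 (child-reported irritation) |

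Item 1 uses one strand of three.

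**Step 2. Follow a pant-area rash through section 7.5.1 to item 1.**

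- *Rash graded by the parent, no care sought:* not an AE or ADE. It reaches item 6 only.
- *Rash that worries the parent, who contacts trial staff as Attachment A advises:* this plausibly counts as normal follow-up within the trial (an inference; the documents do not define the term). If so, it is not an AE or ADE and reaches item 6 only.
- *Rash that leads to withdrawal without outside care:* section 7.5.1 makes no exception for it, so it is not an AE or ADE. Section 3.5.1 requires the reason for withdrawal to be recorded in Subject Accountability, but item 1 does not refer to that record.
- *Rash for which outside medical attention is sought:* documented as an AE or ADE. It enters the item 1 summary if judged product-related.

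Only the last route reaches item 1.

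**Step 3. Look for a link or a limit.** A link would be text that brings items 6 and 10 into the item 1 recommendation. A limit would be text that confines the recommendation to events other than pant-area rash. The visible text of Attachment B, section 2, section 3.1 and section 7.5.1 contains neither. Section 2 combines the strands for the objective but does not say how item 1 fits into that combination. Amendment 1 does not touch item 1.

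**The case against.** **The split is deliberate.** Item 1 stands under General Safety, section 3.1 lists general safety as a domain made up of AEs and ADEs, and Skin Health has its own heading and endpoints. Section 7.5.1 gives a sensible reason for keeping an endpoint out of the AE log. This stands: neither the split nor the exclusion is an error. What it does not settle is that item 1's conclusion speaks of product safety without that restriction.

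**No trial-level conclusion is shown to rest on item 1.** Section 2 calls for the combined evidence, Attachment A refers to the outcome of the trial as a whole, and Attachment B promises descriptive statistics for all parameters. This also stands, and it limits the harm to one recommendation in the report.

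**The link may exist out of sight.** Skin Health has several redacted blocks, and Amendment 2 is listed in the contents but its text was not available. The point can therefore be made only about visible text.

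**Some supporting passages are indirect.** The Introduction's remark on rash risk compares two age groups, not two products. Attachment A's expectation of no safety problems "based on skin and health related AEs" draws on surveillance of similar products, not on this trial's AE definition. Both show that skin matters to safety here; neither shows that the test pant carries more rash.

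**A stronger reading to resist.** A reader might infer that rash goes unanalysed, or that the trial's safety verdict ignores skin. The documents do not support either: items 6 and 10 are planned analyses and section 2 includes skin evidence. Nor can one attach a probability to a wrong conclusion, because item 1 describes a judgement by four roles, not a comparison of event counts.

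**Conclusion.** The point holds for item 1 as visible. Its conclusion is broader than its named data: it claims product safety on AEs and ADEs, from which pant-area rash without outside care is removed by rule, and that rash is the main expected risk. This is a mismatch between a stated recommendation and its evidence, not a flaw in data collection or in the skin analyses.

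It should be fixed, but its reach is limited: the rash and irritation data are collected and analysed in any case, and the primary objective already draws on them. The size cannot be quantified from the documents. The conclusion assumes that the redacted Skin Health text and Amendment 2 contain no rule that links the skin results to item 1; if either does, the point falls away or reduces to a cross-reference.

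**What to change.** **Preferred.** Amend item 1 so that the recommendation on comparable product safety considers three things by product: the AE/ADE summary, the item 6 and item 10 results, and withdrawals due to rash as already recorded in Subject Accountability (section 3.5.1). A descriptive presentation is enough; no new test or margin is needed.

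**Failing that.** Limit item 1's conclusion explicitly to AEs and ADEs other than pant-area rash without outside medical attention, and state that skin safety is judged under Skin Health.

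Either way, reconcile item 1 with section 7.5.1 and section 2, so that all three describe the same scope of safety. If redacted text or Amendment 2 already holds the link, a cross-reference in item 1 suffices.

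**Cost.** The fallback is about one sentence. The preferred change is a wording amendment and a small table from data already collected. The price is a safety summary that may read less favourably if rash turns out worse on the test pant.
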